 - Counsel on need to avoid alcohol, drugs, tobacco and medications throughout the study.
 - Ask subject to remain fasting (water is permitted) for 8 hours prior to returning to the clinic in the morning.

Clinic Visit 04, Day 4

- Vital signs including oral temperature, blood pressure, and pulse will be obtained.
- Review inclusion/exclusion criteria (including assessment of time of last oral food intake).
- A targeted physical exam may be performed, if indicated.
- Review concomitant medications
- Review for AEs and SAEs
- Collect 10 mL of blood for oxfendazole level approximately 24 hours following dosing on day 3 (+/- 2 hours).

Administration of Study Medication

A study nurse will administer a single oral dose of oxfendazole to the subject. Escalating dose levels of 3, 7.5 and 15 mg/kg will be evaluated sequentially.

- Subjects will remain fasting (water is permitted) for two hours after the administration of drug.
- Obtain 10 mL of blood 2 hr after study drug administration (+/- 20 minutes) for oxfendazole levels
- Counsel on need to avoid alcohol, drugs, tobacco and medications throughout the study.
- Ask subject to remain fasting (water is permitted) for 8 hours prior to returning to the clinic in the morning.

Clinic Visit 05, Day 5:

- Vital signs including oral temperature, blood pressure, and pulse will be obtained.
- Review inclusion/exclusion criteria (including assessment of time of last oral food intake).
- A targeted physical exam may be performed, if indicated.
- Review concomitant medications
- Review for AEs and SAEs
- A heparin lock will be inserted, blood will be drawn (10 mL) for oxfendazole levels prior to study drug administration -approximately 24 hours after dosing on day 4 (+/- 2 hours)

-
- Collect 15 mL of blood for safety panels (hemoglobin, white blood cell count, including neutrophil count, platelet count, INR, partial thromboplastin time, Na, K, Cl, CO₂, blood urea nitrogen, creatinine, ALT, AST, and total bilirubin).
 - Collect urine for dipstick testing for protein and glucose.

Administration of Study Medication

A study nurse will administer a single oral dose of oxfendazole to the subject. Escalating dose levels of 3, 7.5 and 15 mg/kg will be evaluated sequentially.

- Subjects will remain fasting (water is permitted) for two hours after the administration of drug.

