- Lunch and dinner will be provided. Subjects will be allowed to eat snacks but will be asked to avoid drinking grapefruit juice and excessive (>2 cups) coffee.
- 10 mL of blood for oxfendazole level will be drawn predose and at 30 minutes, 1, 2, 3, 4, 6, 9, and 12 hours (all times have a window of +/- 15 minutes except the 9 and 12 hour samples which have a window of +/- 30 minutes- it is critical to record the exact time of blood draw).
- Obtain EKG 2 hr after study drug administration (+/- 20 minutes)
- Assess AEs and SAEs throughout the day and prior to discharge from the CRU.
- Counsel on need to avoid alcohol, drugs, tobacco and medications throughout the study.
- Counseling on avoidance of pregnancy.
- Ask subject to remain fasting (water is permitted) for 8 hours prior to returning to the clinic in the morning.

Clinic Visit 06, Day 6

- Vital signs including oral temperature, blood pressure, and pulse will be obtained.
- A targeted physical exam will be performed if indicated
- Review concomitant medications
- Review for AEs and SAEs.
- Counsel on need to avoid alcohol, drugs, tobacco and medications throughout the study.
- Collect 10 mL of blood for oxfendazole level approximately 24 hours after dosing on day 5 (+6 hours)

Clinic Visit 07, Day 8 (+/- 1 day)

- Vital signs including oral temperature, blood pressure, and pulse will be obtained.
- A targeted physical exam may be performed, if indicated.
- Review concomitant medications
- Review for AEs and SAEs.
- Counsel on need to avoid alcohol, drugs, tobacco and medications throughout the study.
- Collect 10 mL of blood for oxfendazole level
- Collect 15 mL of blood for safety panels (hemoglobin, white blood cell count, including neutrophil count, platelet count, INR, partial thromboplastin time, Na, K, Cl, CO₂, blood urea nitrogen, creatinine, ALT, AST, and total bilirubin).

-
- Collect urine for dipstick testing for protein and glucose.
 - An EKG will be performed and will be reviewed by a cardiologist.

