Days 3 and 4: 10 mL blood prior to study drug administration-approximately 24 hours after dosing on previous day (+/- 2 hours)

Day 6: 10 mL blood-approximately 24 hours after dosing on previous day (+6hours)

Group 4		Follow Up Visits								
		Screening Study Visit 00	Baseline Study visit 01	Study Visit 02	Study Visit 03	Study Visit 04	Study Visit 05	Study Completion Study Visit 06	Unscheduled Visit	Early Termination Visit
Study Day		D-28 to -1	D1	D2	D4	D8	D9	D14		
Visit Window		N/A	N/A	N/A	N/A	+/-1	N/A	+/-2		
Signed Consent Form		X								
Assessment of Eligibility Criteria		X	X			X				
Randomization/Enrollment			X							
Review of Medical History		X	X						X	X
Review of Concomitant Medications		X	X	X	X	X	X	X	X	X
Administration of Study Medication			X			X				
Physical Examination	Complete	X	X							
	Symptom-Directed			(X)	(X)	(X)	(X)	(X)	(X)	X
	Vital Signs	X	X	X	X	X	X	X	(X)	X
Assessment of Adverse Events and SAEs			X	X	X	X	X	X	X	X
Clinical Laboratory	Chemistry	X	X		X			X		X
	Hematology	X	X		X			X		X
	Coagulation Studies	X	X		X			X		X
	Serology	X								
	Urinalysis	X	X		X			X	(X)	X
	Pregnancy Test	X	X			X				
Research Laboratory	PK Studies 10 mL whole blood		X	X		X	X	X		X
Other Procedures	EKG	X	X			X				

(X) – As indicated/appropriate

Hematology – Hemoglobin, WBC and neutrophil count, platelet count.

Biochemistry – **Screening**: creatinine, ALT, AST, random glucose, total bilirubin.

– **Follow Up Visits**: creatinine, sodium, potassium, chloride, carbon dioxide, blood urea nitrogen ALT, AST, total bilirubin.

Coagulation Studies– INR and partial thromboplastin time (PTT)

Serology – Hepatitis B surface antigen, hepatitis C antibody, human immunodeficiency virus (HIV)

Urinalysis – Urine Dipstick for protein and glucose

Research Laboratory – **Days 1 and 8**: 10 mL blood for baseline PK (prior to drug administration), 10 mL blood at 30 minutes, 1, 2, 3, 4, 6, 9, and 12 hours (all times have a window of +/- 15 minutes except the 9 and 12 hour samples which have a window of +/- 30 minutes)

Day 2 and 9: 10 mL blood –approximately 24 hours following study drug dose (+/- 4 hours)

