2.3. PK Sampling Schedule Treatment Groups

For the first phase of the study (Groups 1-3), 10 mL of blood for oxfendazole level will be drawn pre-dose and at 30 minutes, 1, 2, 3, 4, 6, 9, and 12 hours following the first dose. All times have a window of +/- 15 minutes except the 9 and 12 hour samples which have a window of +/- 30 minutes. On Days 2, 3, and 4, blood will be sampled for oxfendazole level approximately 24 hours (+/- 4 hours for Day 2, +/- 2 hours for Days 3 and 4) after the prior dose, but before the current study day dose. On Days 2, 3, and 4, approximately 2 hours (+/- 20 minutes) after administration of study drug, blood will be drawn for oxfendazole level. On Day 5, blood will be sampled pre-dose (24 hours +/- 2 hours after the prior dose) and at 30 minutes, 1, 2, 3, 4, 6, 9, and 12 hours (all times have a window of +/- 15 minutes except the 9 and 12 hour samples which have a window of +/- 30 minutes). Blood will also be sampled for oxfendazole level on Day 6, approximately 24 hours after dosing on Day 5 (+/- 6 hours) and Days 8 (+/- 1 day) and 10 (+/- 2 days).

In the second phase of the study (Group 4), blood sampling for oxfendazole level will be performed pre-dose and at 30 minutes, 1, 2, 3, 4, 5, 9, 12 and 24 hours following each dose on Day 1 and Day 8 (+/- 1 day). All times have a window of +/- 15 minutes except the 9 and 12

hour samples which have a window of \pm 0 minutes and the 24-hour sample which has a window of \pm 4 hours. Blood will also be sampled for oxfendazole level on Day 14 (\pm 0 days).

The exact time for all blood draws for oxfendazole level will be recorded and used for pharmacokinetic noncompartmental analysis (NCA).

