3.4. Definition and Estimation of Individual PK Parameters

The PK parameters listed below will be estimated through a NCA using version 8.0 of Phoenix WinNonlin (Pharsight Corporation, Cary, NC). Actual post-dose time will be used for the estimation of PK parameters instead of nominal time. Subject-specific PK parameters will be presented (Table 16, Table 17, Table 18, Table 19, Table 20, Table 21, Table 22 Table 27, Listing 3, Listing 4, and Listing 5).

Phoenix WinNonlin NCA will use the following settings to compute parameters from plasma PK data:

- Linear Up Log Down calculation method
- Uniform weighting
- Extravascular dose
- Lambda Z Acceptance Criteria
 - o Rsq adjusted ≥ 0.85
 - Span ≥ 1.5 half-lives

\mathbf{C}_{max}

Maximum concentration (C_{max}) is defined as the maximum observed drug concentration observed over all PK sample concentrations for a given dose, and will be obtained from the **Cmax** parameter calculated by Phoenix WinNonlin.

Ctrough

Pre-dose trough concentration (C_{trough}) is defined as the drug concentration observed at the last planned timepoint prior to dosing. Since there is no dose following Day 5, C_{trough} for that day is defined as the concentration 24 hours (nominal time) after dosing.

Tmax

Time of maximum concentration (T_{max}) is defined as the time at which the maximum concentration occurs within the given dosing interval and will be obtained from the **Tmax** parameter calculated by Phoenix WinNonlin.

λ_z

The terminal phase elimination rate constant (λ_z) is defined as the first-order rate constant describing the rate of decrease of drug concentration in the terminal phase (defined as the terminal region of the PK curve where drug concentration follows first-order elimination kinetics), and will be obtained from the **Lambda z** parameter calculated by Phoenix WinNonlin.

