3.5.3. Attainment of Steady State

Attainment of steady state by Dose 5 will be assessed by visual examination of the concentration versus time plots (Figure 1, Figure 2, Figure 3, Figure 4, Figure 5, and Figure 6).

Graphical findings will be supported by statistical comparison of C_{max} and C_{trough} values on Day 5 with the corresponding values on Day 4 and Day 3. C_{max} and C_{trough} will be log-transformed and analyzed using the following mixed effects model for Y_{ijk} , the log-transformed exposure parameter observed on the kth subject on day j of dose group i:

$$Y_{ijk} = \mu + \pi_j + \lambda_i + \tau_{d[i,j]} + s_{ik} + \varepsilon_{ijk}$$

where μ is the intercept; π_j is a fixed effect associated with day j; λ_i is a fixed effect associated with dose group i, $\tau_{d[i,j]}$ is a fixed effect associated with the interaction of day j and dose group i; s_{ik} is a random effect associated with the kth subject in dose group i, and e_{ijk} is a random error term with mean 0 and variance σ_e^2 . This model will be fit using restricted maximum likelihood estimation (REML) in SAS PROC MIXED, with the Kenward and Roger denominator degrees of freedom. Covariance structure will be selected based on AIC, from the following candidate structures: variance components, first-order autoregressive, compound symmetry, Toeplitz, and unstructured. SAS code will be similar to:

PROC MIXED;

CLASS DAY DOSEGROUP SUBJECT;

MODEL LCMAX = DAY DOSEGROUP DAY*DOSEGROUP / DDFM=KR;

RANDOM SUBJECT / TYPE = VC;

LSMEANS DAY*DOSEGROUP / PDIFF CL;

RUN;

The mean difference in log-transformed parameter (C_{max} or C_{trough}) between Day 5 and each of Days 4 and 3 at each dose level will be back transformed to obtain the geometric mean ratio. Contrasts of model parameters will be used to generate 95% confidence intervals for the geometric mean ratios. The geometric mean ratios and corresponding confidence intervals will be graphically depicted in Figure 25 and reported in Table 26, alongside the p-value for the hypothesis test of no difference in log-transformed C_{max} and C_{trough} between Day 5 and each of Days 4 and 3 at each dose level.

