¹ Peak concentration is shown in this table as concentration at 2 hours (nominal time) after the corresponding dose.

Table 10: Peak and Trough Concentrations by Dose: Group 2 (7.5 mg/kg)

Table 11: Peak and Trough Concentrations by Dose: Group 3 (15 mg/kg)

Table 10 and **Table 11** will use the form of **Table 9** to display corresponding data for Group 2 and Group 3.

² Trough concentration is shown in this table as concentration at 24 hours (nominal time) after the corresponding dose.

³ Number of data points used to compute the summary statistics. BQL values were imputed as 0 if they did not come after a PK sample concentration that is above the LLOQ and treated as missing otherwise.

Table 12: Individual Concentrations and Summary Statistics by Nominal Time: Group 4 Sequence A, Period 1 (3mg/kg, Fasted)

| | | Nominal Time After Dose (hours) | | | | | | | | | | |
|------------|--------------|---------------------------------|--------|--------|--------|--------|--------|--------|--------|--------|--|--|
| Subject ID | Pre- dose | 0.5 | 1 | 2 | 3 | 4 | 6 | 9 | 12 | 24 | | |
| 99ZZZ001 | х | Х | Х | X | X | Х | X | X | X | X | | |
| 99ZZZ002 | х | Х | Х | X | X | Х | X | X | X | X | | |
| 99ZZZ003 | х | Х | Х | X | X | Х | X | X | X | X | | |
| | х | Х | Х | X | X | Х | X | Х | X | X | | |
| Statistic | | | | | | | | | | | | |
| N^1 | х | х | Х | Х | X | Х | Х | Х | X | X | | |
| Mean | x.x | X.X | X.X | x.x | x.x | X.X | x.x | x.x | X.X | X.X | | |
| SD | x.x | x.x | X.X | x.x | x.x | X.X | x.x | x.x | x.x | X.X | | |
| GM | x.x | X.X | X.X | X.X | X.X | X.X | X.X | X.X | X.X | X.X | | |
| (Min, Max) | (x, x) | (x, x) | (x, x) | (x, x) | (x, x) | (x, x) | (x, x) | (x, x) | (x, x) | (x, x) | | |

¹ Number of data points used to compute the summary statistics. BQL values were imputed as 0 if they did not come after a PK sample concentration that is above the LLOQ and treated as missing otherwise.

Table 13: Individual Concentrations and Summary Statistics by Nominal Time: Group 4 Sequence A, Period 2 (3mg/kg, Fed)

| | Nominal Time After Dose (hours) | | | | | | | | | | |
|------------|---------------------------------|--------|--------|--------|--------|--------|--------|--------|--------|--------|--------|
| Subject ID | Pre- dose | .5 | 1 | 2 | 3 | 4 | 6 | 9 | 12 | 24 | 144 |
| 99ZZZ001 | X | X | X | X | X | X | X | Х | X | Х | X |
| 99ZZZ002 | X | X | X | X | X | X | X | Х | X | Х | X |
| 99ZZZ003 | X | X | X | X | X | X | X | Х | X | Х | X |

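### The steady-state comparison sets a Day 5 trough that the protocol lets be drawn up to 6 h late against Day 3 and Day 4 troughs drawn at 24 ± 2 h, with no adjustment for draw time; the harm is small

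*SAP*

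**What the plan says.** SAP 3.4 defines the Day 5 trough through the Day 6 sample: "Since there is no dose following Day 5, C_{trough} for that day is defined as the concentration 24 hours (nominal time) after dosing". The footnote to SAP Table 9 uses the same convention for every dose: "Trough concentration is shown in this table as concentration at 24 hours (nominal time) after the corresponding dose".

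The documents disagree on when the Day 6 sample may be drawn:
- Protocol 7.3, Clinic Visit 06: "approximately 24 hours after dosing on day 5 (+6 hours".
- Protocol Appendix A, Groups 1-3: "approximately 24 hours after dosing on previous day (+6hours".
- SAP 2.3: "approximately 24 hours after dosing on Day 5 (+/- 6 hours".

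The comparator troughs have a tighter, two-sided window. Protocol 7.3 places the Day 4 trough "approximately 24 hours after dosing on day 4 (+/- 2 hours" and the Day 3 trough "approximately 24 hours following dosing on day 3 (+/- 2 hours". SAP 2.3 agrees with both.

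SAP 3.5.3 makes visual examination of the concentration plots the main assessment of steady state, then adds: "Graphical findings will be supported by statistical comparison of C_{max} and C_{trough} values on Day 5", set against Days 4 and 3. The model has day, dose group, their interaction and a random subject effect. Under SAP 3.5.2, sex is the only covariate that may be added. Ratios, 95% confidence intervals and p-values by dose level go into Table 26 and Figure 25.

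**The concern.** At 24 h the concentration is falling, so a sample taken later reads lower. The Day 3 and Day 4 draws can be early or late by the same amount, and their timing errors average out. Under the protocol window the Day 6 draw can only be on time or late, so its error does not. The day term in the model then carries both the pharmacokinetics and the sampling schedule, and no planned output separates them.

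Using actual times in the non-compartmental analysis does not help, because a trough is an observed value and nothing moves it to 24 h. Listing 3 prints actual times but marks only out-of-window draws, so a sample at 28 h would be in window under either document and would pass unmarked. At stake is an apparent fall in trough on Day 5 in Table 26, with an interval and p-value that could disagree with the plots.

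**Working it through.** The plan gives no figure for this comparison, so there is none to reproduce.

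**Inputs from the documents.** Half-life 8.5-11 h (Protocol 2.1.2, single-dose data; applying it to repeated dosing is an assumption). Eight subjects per group. Windows as quoted above.

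**Assumptions not in the documents.** Draw times uniform within the window; within-subject log SD 0.10 to 0.30.

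**Step 1: what the true ratio should be.** With r = 2^(−24/t½) and linear superposition:
- Day 5/Day 4 = (1 − r⁵)/(1 − r⁴) = 1.0003 (8.5 h) to 1.0018 (11 h)
- Day 5/Day 3 = (1 − r⁵)/(1 − r³) = 1.003 to 1.010

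Superposition is approximate, because single-dose exposure was non-linear. On these figures there is almost no real change for the comparison to find.

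**Step 2: effect of one late draw.** A draw h hours late reads low by 1 − 2^(−h/t½). For 1 h this is 6.1% (11 h) to 7.8% (8.5 h); for 2 h, 11.8% to 15.0%.

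**Step 3: bias in the geometric mean ratio.** The comparator windows are symmetric, so the bias factor is exp(−λ × mean delay), with λ = ln 2/t½ = 0.0630 to 0.0815 per hour. A uniform 0 to w window has mean delay w/2:
- 0.5 h: 0.960 to 0.969
- 1 h: 0.922 to 0.939
- 3 h: 0.783 to 0.828

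**Step 4: error rate of the 95% interval.** Simulation at the Step 1 ratios: three groups of eight, Days 3 to 5, Day 3 and Day 4 draws uniform within ± 2 h, subject plus day-by-group model, pooled residual on 42 df. Ranges cover both half-lives and log SD 0.10 to 0.30.

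| Day 6 draws | Day 5/Day 4 ratio | Intervals excluding 1 | At log SD 0.20 |
|---|---|---|---|
| 0 to +1 h | 0.96-0.97 | 5-8% | 6% |
| 0 to +2 h | 0.92-0.94 | 7-23% | 9-11% |
| 0 to +6 h | 0.78-0.83 | 21-88% | 39-55% |
| ± 6 h | 1.00 | 6-8% | 6-7% |

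The title of Figure 25 puts Days 3 and 4 over Day 5. In that direction the first three rows read 1.03-1.04, 1.06-1.08 and 1.21-1.28.

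In the last row the timing error has no mean effect but adds noise. The SD of a uniform ± 6 h draw is 12/√12 = 3.46 h. Multiplied by λ this is a log SD of 0.22-0.28, against 0.07-0.09 for ± 2 h.

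**Step 5: does interpolation work?** Taking the log-linear value at 24.0 h from the 12 h and Day 6 samples when the draw is late, and from the Day 6 and Day 8 samples when it is early, gives a ratio of 1.00 with 3-5% of intervals excluding 1 under every window in the table (mono-exponential decline, independent error on each sample). Correcting late draws only, under ± 6 h, gives 1.10-1.13 with 9-35% excluding 1.

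**Step 6: is the Day 8 sample usable?** Protocol 2.1.2 gives 943.9 ng/mL as the lowest dose-group geometric mean Cmax, with median Tmax 2 h. At 72 h and the shorter half-life, 943.9 × 2^(−70/8.5) ≈ 3.1 ng/mL, about six times the 0.5 ng/mL quantification limit in SAP 2.4. At 96 h, the end of the Day 8 window, it is 943.9 × 2^(−94/8.5) ≈ 0.44 ng/mL, so an occasional value may fall below the limit.

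**The case against.** - **Short delays are the likely case.** Subjects are told on Day 5 to return in the morning. With draws 0 to 1 h late the error rate is 5-8% against a nominal 5%. This stands. A reader might infer from the 0 to +6 h row that Table 26 will wrongly reject steady state about half the time. The documents do not support that: nothing suggests draws spread evenly over six hours, and the row is an upper bound.
- **The bias exists under only one of two conflicting windows.** This also stands. The firm defect is the contradiction; the bias depends on how it is resolved and on how late the draws are.
- **The simulation is not the SAP's full procedure.** SAP 3.5.3 uses Kenward-Roger degrees of freedom and chooses among five covariance structures by AIC, which could absorb unequal Day 5 variance. The percentages are therefore approximate. A covariance structure cannot remove a shift in the mean, so the ratios are unaffected.
- **The SAP gives some visibility.** Listing 3 shows actual times, SAP 3.3 promises discussion of special cases, and SAP 3.5.2 calls for model diagnostics. A careful reader could see a late draw, but none of this corrects the comparison.
- **The trough could be read as the draw before the same day's dose.** This changes nothing on timing: those Day 3 and Day 4 draws are also ± 2 h, and Day 5 is still the Day 6 sample.

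**Conclusion.** The point holds, at low severity. The Day 6 window differs between protocol and SAP, and SAP 3.5.3 has no rule for trough draw time. If the late-only window applies, the Day 5/Day 4 ratio is biased below 1 by 3-4% for draws 0 to 1 h late, 6-8% for 0 to 2 h, and at most 17-22% for draws spread over 0 to 6 h. If the SAP's window applies, there is no mean bias. The sizes rest on the single-dose half-life and assumed uniform draw times; the error rates rest also on an assumed log SD of 0.10-0.30 and a simpler model than the SAP's.

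A reader might go further and conclude that the steady-state assessment as a whole, the accumulation ratios or the escalation decisions are compromised. They are not. Visual examination remains the main method. AUCτ is a partial area computed on actual times. The trough is not a listed endpoint (Protocol 3.2), and escalation rests on safety events (Protocol 9.5.2). What is affected is one supportive comparison in Table 26 and Figure 25.

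**What to change.** 1. Reconcile the Day 6 sampling window between Protocol 7.3 and Appendix A on one side and SAP 2.3 on the other.
2. In SAP 3.5.3 only, use the Day 5 trough at 24.0 h by log-linear interpolation on actual times, whichever window is adopted. If the Day 6 draw is late, interpolate between the 12 h and Day 6 samples; if early, between the Day 6 and Day 8 samples. Where the Day 8 sample is not quantifiable, keep the observed value and flag it. Do not adopt a rule that corrects late draws and leaves early ones alone.
3. Report the same comparison on observed values alongside, and keep the observed trough in the parameter tables, in line with Protocol 11.4.4.

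A subset analysis limited to 24 ± 2 h is not needed. It would not cure the late-only case, since the draws kept would be 0 to +2 h and the ratio would stay at 0.92-0.94.

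The cost is a few SAP sentences and a short derivation; exact draw times are already to be recorded. The downside is that some compared values become derived, and they read slightly high if the decline is bi-exponential. With assumed fast half-lives of 3-6 h and slow ones of 8.5-24 h, the excess for a late draw is about 0.2-1.4% at 1 h and 0.3-2.7% at 2 h, depending on the assumed mix of phases. Uncorrected, the same draws read 3-9% and 6-16% low.

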3.5. Descriptive Statistics and Inference of PK Parameters

3.5.1. Pharmacokinetic Parameter Summaries

All PK parameters will be summarized using descriptive statistics: N, Mean, standard deviation (SD), Min, Max, Median, coefficient of variation as a percent (CV %), and geometric mean (GM). A subset of PK parameters will be summarized by dose and dose group where appropriate (Table 16, Table 17, Table 18, Table 19, Table 20, and Table 21). Group 4 parameters will be summarized by condition (Table 22).

